5.2 Descriptive statistics

Tables of demographic characteristics of participants in the PreTRM® and historical control groups will be created from the study data bases. Baseline subject characteristics include: demographic information, medical history, physical examination, and other laboratory tests. Comorbidities include risk factors, diabetes mellitus, or metabolic syndrome, among others. Tables of resource use of prospective subjects and historical control groups will be created as well. Variables will be summarized using means, medians, ranges, interquartile ranges and standard deviations for continuous data and counts and percentages for categorical data. In addition, we will also summarize the percentage of prospective subjects classified as higher and not-higher risk from the PreTRM® test results. Summaries will be created for both the mITT population and separately for the ITT population, and for the higher and not-higher risk groups in the mITT population.

5.3 Covariate Analyses

The prospective participants and historical controls in the study may differ in ways other than the interventions or exposures under investigation. Covariates will be used to adjust the regressions prespecified in the primary analysis for potential differences between the control and prospective arms, and in derivation of propensity scores used to adjust for biases between the two arms, either by weighting subjects in the alternative analysis or by matching subjects in exploratory analyses..

The following variables are candidates for inclusion as covariates in the primary analysis: regression with covariates. These baseline covariates are present before blood draw.

- Maternal age
- Categorical parity: multiparous vs. nulliparous
- Maternal substance use disorders assessed as Neonatal Opioid Withdrawal Syndrome

The following variables are candidates for inclusion as covariates in the alternative analysis using inverse probability score weighting, and in the exploratory analysis using propensity matching. These baseline covariates are present before blood draw.

- Maternal age
- Categorical parity (nulliparous vs. multiparous)
- Gravidity (integer)
- Number of term children
- Number of miscarriages
- Maternal race
- Pre-pregnancy continuous BMI
- Pre-pregnancy categorical low BMI<19
- Maternal height
- Maternal chronic hypertension
- Gestational diabetes
- Insurance status
- Smoking status
- Maternal substance use disorders assessed as Neonatal Opioid Withdrawal Syndrome
- Delivery outside of ChristianaCare

Inclusion of covariates in the covariate-adjusted primary, alternative and exploratory analyses will depend on the proportion of missing values for the covariate, as follows. For each candidate variable, if fewer than 1% of subjects have a missing value, that variable will be included as a covariate in the analysis. Sensitivity of results to missing data will be examined using missing data analysis methods.

The primary and alternative analyses will use cases with complete data for the included covariates, provided that no more than 5% of the total subjects are excluded from the analysis. If more than 5% of the total subjects would be excluded from the analysis,

candidate variables will be dropped from the analyses in order of the percent missing, until no more than 5% of the total subjects are excluded from the analysis.

Descriptive statistics on baseline covariates will be compared between the prospective arm and historical controls. This analysis includes covariates prespecified for both the primary and alternative analyses. If we can obtain information on some of the covariates that affect exposures and decisions to participate, we can assess our ability to reduce bias. Sociodemographic factors such as education and age are often considered in this role.

It is common that the basic characteristics may not be balanced between the prospective cohort and historical cohort groups. We will examine the potential sources of bias and address them with a classical and common technique—adjusting by covariates.

While an easy to implement strategy to control for selection bias in propensity scoring is to adjust for factors that can break the biasing paths linking the exposure and the outcome, regression with covariates benefits from adjustment for independent predictors of the outcome. We expect that adjustment for independently predictive covariates can result in decreased selection bias and increased precision.

The factors which impact the effect of intervention through selection and epoch biases will be assessed to demonstrate how well they address confounding in the analysis. Model selection techniques will be used to demonstrate an optimized model. Although a minimum set of covariates is prespecified for use in addressing confounding, there may be an advantage in exploratory analyses to using a staged approach in which groups of covariates are introduced sequentially leading to progressively greater adjustment. Using random forest and other machine learning methods, we will provide insight into which covariates have relatively greater influences on effect estimates, permitting comparison with known or expected associations or permitting the identification of possible mediator and/or intermediate variables.

In alternative and exploratory analyses, the propensity score model will model the propensity score: predicted probability of a participant who will be placed in the prospective group, via running logistic regression: the dependent variable,

$y=1$, if prospective group;

$y=0$, if historical group.

The propensity score model will be derived from logistic regression using the key clinical covariates available at the gestational age of PreTRM® blood draw in the historical cohort, as well basic demographic characteristics. The variables used to generate propensity scores are specified above.

The performance of the propensity score model will be evaluated by AUC/ROC c-index; potential interaction terms or high degree of terms may be included to improve the performance of the propensity model. We will obtain an estimation for the propensity score: predicted probability (p).

With propensity score methods, we will check whether covariates are balanced across the prospective and historical cohorts. We can examine the distribution of propensity score between groups. We will assess covariate balance between groups using p-value for comparison of two group, as well absolute standardized mean difference (ASMD), with an ASMD <0.1 indicating good balance.

We propose Inverse Propensity score Weighting (IPW) method for the alternative analysis. IPW is a statistical technique for calculating statistics standardized to a pseudo-population different from that in which the data was collected. After obtaining propensity score, we define for the prospective arm:

$$IPW = \frac{1}{PS}; \quad IPW = \frac{1}{PS}; \quad \text{for historical controls: } IPW = \frac{1}{1-PS}.$$

$IPW = \frac{1}{1-PS}$. To avoid the IPW method's instability to extremes of propensity among participants with high propensity score weights with undue influence the results, we will use truncated scores and weights: 1) below the 1st or 5th percentile and above the

99th or 95th percentile; resulting in weights between reasonable intervals for all participants; 2) truncating propensity score <0.001 or >0.999.

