3.7 Definitions of Outcomes

Primary and secondary endpoints, including adverse events, will be collected, measured, calculated, and pre-defined according to the study design.

- Composite neonatal morbidity and mortality (NMI): neonatal morbidity and mortality (14). Neonates are assigned points according to the following criteria.
0 to 4 scale with NICU
 - 0 = no events,
 - 1 = one event for (RDS, BPD, grade III or IV IVH, PVL, proven sepsis, or NEC) or <5 days in the NICU, and no perinatal mortality;
 - 2 = two events or between 5 and 20 days in the NICU, and no perinatal mortality;

3 = three or more events or >20 days in the NICU, and no perinatal mortality;

4 = perinatal mortality

The component condition abbreviations are defined as follows:

RDS: respiratory distress syndrome

BPD: bronchopulmonary dysplasia

IVH: intraventricular hemorrhage

NEC: necrotizing enterocolitis

PVL: periventricular leukomalacia

Component conditions are further defined in Appendix 1.

- Length of neonatal hospital stay (NNOLOS): days from delivery to neonatal discharge home, or until death if occurring before discharge. This includes all levels of care before discharge home, including all transfers across levels of care. NNOLOS will be calculated in fractional days if times of birth and discharge are available and rounded to the nearest integer, or as the number of days of difference between dates if times are not available; times are not required. In cases of stillbirth or neonatal mortality prior to discharge home, NNOLOS is set to one day longer than the maximum length of stay recorded for any infant. NNOLOS will be truncated at $44^{0/7}$ weeks of gestational age as specified in the protocol.

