5.1 Analysis Populations

One control population will be considered in primary analyses: the historical control population. The historical control population includes all subjects who attended ChristianaCare during the eligibility period and who satisfy all eligibility criteria.

The historical control arm will be the control population for primary and alternative analysis of the primary, secondary and exploratory endpoints.

Seven subject populations will be considered in the analyses: an Intent-to-Treat (ITT) population, a modified ITT population, a completer(s) population, a compliant completers population, a non-intervention completers population and a safety population. The completers, compliant completers, non-intervention completers and modified ITT populations are subsets of the ITT population.

The ITT population includes all historical subjects selected and all prospective patients enrolled regardless of whether or not the co-primary outcomes were observed, or in the prospective arm, any PreTRM test result has been generated or intervention consent has been signed. Subjects with missing outcomes will be handled as described in the missing data sensitivity analyses.

The modified ITT (mITT) population includes all subjects for whom both co-primary outcomes are known; and who have either been selected for the historical control group, received a not-higher-risk PreTRM® test result, or consented to and initiated treatment before 24^{0/7} weeks gestation after receiving a higher risk PreTRM® test result.

The completers population includes subjects for whom both of the co-primary outcomes are known, and, in the prospective arm, for whom a PreTRM® test result was generated.

The compliant completers population includes ITT subjects who have missed no more than 20% of daily doses for both low-dose aspirin and vaginal progesterone, and participated in weekly care management calls with no more than 20% missed weeks.

The non-intervention completers population includes all ITT subjects who received a higher-risk PreTRM® test result but neither consented to nor initiated treatment before 24^{0/7} weeks gestation.

The safety population includes all eligible subjects who gave consent to participate in the study and attempted a blood draw for the PreTRM® test, regardless of receipt of study interventions.

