APPENDIX I:

DEFINITIONS OF NEONATAL MORBIDITY/MORTALITY

Neonatal Death and Stillbirth: Intrauterine fetal demise at a viable gestational age or neonatal death within 28 days of delivery

Intraventricular Hemorrhage (IVH): determined by cranial ultrasound or computed tomography

Grade I	subependymal hemorrhage
Grade II	intraventricular hemorrhage, uncomplicated
Grade III	intraventricular hemorrhage with ventricular dilatation
Grade IV	intraventricular hemorrhage with ventricular dilatation and parenchymal extension

Periventricular Leukomalacia (PVL): all PVL is determined by cranial ultrasound

- Any PVL
- Cystic PVL

Necrotizing Enterocolitis (NEC)

Stage I: Other – Suspect

• Treatment was observation

Stage II: Clinical – Definite

• Treatment was medical

Stage III: Surgical – Advanced

• Treatment was surgical

Respiratory Distress Syndrome (RDS): requires both diagnosis and oxygen therapy

- For the purpose of the study diagnosis must include:
 - oxygen therapy ($\text{FiO}_2 \geq 0.40$) until infant death or ≥ 24 hours **and**
 - a clinical diagnosis of RDS

Retinopathy of Prematurity (ROP)

- Stage I Ophthalmoscopic demarcation line of normal and abnormal vessels
- Stage II Intra-retinal ridge (ridge that rises from the retina as a result of the growth of the abnormal vessels)
- Stage III Ridge with extraretinal fibrovascular proliferation (the ridge grows from the spread of the abnormal vessels and extends into the vitreous)
- Stage III+ Stage III and “plus disease” meaning that the blood vessels of the retina have become enlarged and twisted, indicating a worsening of the disease.
- Stage IV Partially detached retina.
- Stage V Complete retinal detachment.

Bronchopulmonary Dysplasia (BPD)

- Treatment with $> 21\%$ oxygen for at least 28 days, **or**
- Oxygen dependence after 36 weeks post-conceptional age

Sepsis: Must include

- Blood culture proven sepsis, **and**
- a Clinically ill infant with infection defined as:
 - Bacterial sepsis of the newborn
 - Streptococcal sepsis
 - Severe sepsis

Neonatal Seizure

- Any incident(s) documented as evidence of seizure/epileptic activity by the neonatal staff,

DEFINITIONS OF COMPOSITE PERINATAL MORTALITY/NEONATAL MORBIDITY OUTCOME SCORES:

0 to 4 scale with NICU* (NMI): This score is defined as the following:

0 = no events,
1 = one event for (RDS, BPD, grade III or IV IVH, any PVL, proven sepsis, or NEC) or <1-4 days in the NICU, and no perinatal mortality;

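### Delivery site and newborn-assessed substance use do not fit the SAP's statement that covariates precede the blood draw, and NOWS handling in stillbirths is not fixed

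*SAP*

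**What the plan says.** Section 5.3 gives two candidate lists and introduces each with the sentence "These baseline covariates are present before blood draw". The draw takes place at 19 1/7 to 20 6/7 weeks (sections 3.3 and 3.4).

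- The primary list has three entries: maternal age, parity, and "Maternal substance use disorders assessed as Neonatal Opioid Withdrawal Syndrome".
- The longer list, for inverse probability weighting and matching, repeats these and adds others, among them "Delivery outside of ChristianaCare".

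For the propensity model, section 5.3 adds: "The propensity score model will be derived from logistic regression using the key clinical covariates available at the gestational age of" the PreTRM blood draw.

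On missing covariates, section 5.3 includes a candidate if fewer than 1% of subjects lack a value. It then says "The primary and alternative analyses will use cases with complete data for the included covariates", provided that no more than 5% of subjects are lost.

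On stillbirth, section 3.7 says "In cases of stillbirth or neonatal mortality prior to discharge home, NNOLOS is set to one day longer than the maximum length of stay" (the longest stay seen among all infants). Perinatal mortality scores NMI 4, and Appendix I defines neonatal death and stillbirth as "Intrauterine fetal demise at a viable gestational age or neonatal death within 28 days of delivery". Section 5.1 says that the modified ITT (mITT) population "includes all subjects for whom both co-primary outcomes are known" and who also meet its conditions on arm, test result and treatment.

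**The concern.** The comparison is not randomised, so the case for a treatment effect leans heavily on the adjustment set. Two entries do not fit the stated timing.

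Delivery site is settled at birth. In a propensity model it can carry effects of the intervention, or of how outcomes were ascertained, into the weights and matches that are meant to remove baseline differences.

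NOWS is ascertained in a live newborn, during the stay that NNOLOS measures. It cannot be assessed in a stillbirth, and an early death may leave it unassessed. The SAP does not say whether such births count as unexposed or as missing. Because NOWS is a primary covariate and the primary analysis uses complete cases, that coding choice could decide whether the worst outcomes stay in the primary model.

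**Working it through.** **Timing, set side by side**

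| Covariate | List | Known at about 20 weeks? | Conflict |
|---|---|---|---|
| Delivery outside ChristianaCare | Propensity only | No, known at birth | Contradicts the timing sentence and the propensity-model sentence |
| Maternal substance use, assessed as NOWS | Primary and propensity | The disorder possibly; the measure no | Contradicts the propensity-model sentence; the timing sentence is imprecise |

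**How a stillbirth could leave the primary model**

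1. It scores NMI 4 and has NNOLOS at the maximum plus one day, so both co-primaries are known.
2. It can therefore be in mITT (section 5.1).
3. NOWS cannot be assessed. The SAP gives no coding rule, and section 5.10 has only general missing-at-random text.
4. If NOWS is coded missing and fewer than 1% of subjects lack it overall, section 5.3 keeps NOWS in the model.
5. The complete-case rule then deletes the birth. If NOWS is coded absent at step 4, nothing is deleted.

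**Births at stake if step 4 applies (illustration only)**

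Inputs: 1,453 prospective subjects, about 10,000 controls, 34% higher risk, 55% compliance, preterm birth rate 9.1%, and NMI>=3 rates of 0.020-0.023 prospective and 0.036 control (all section 4). Assumptions: 55% approximates treatment uptake; the planning rates apply to mITT; the stillbirth rate, which the SAP does not give, is 0.2-0.6%.

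- Prospective mITT: 1,453 × 0.66 + 1,453 × 0.34 × 0.55 = 959 + 272 = 1,231.
- Total: 1,231 + 10,000 = 11,231. The 1% limit is 112.3, so NOWS is sure to be included with up to 112 missing values.
- Stillbirths: 0.002 × 11,231 = 22.5 and 0.006 × 11,231 = 67.4 (about 2-7 prospective and 20-60 control).
- Planned NMI>=3 births: 0.036 × 10,000 = 360, plus 0.020 × 1,231 = 25 or 0.023 × 1,231 = 28, giving 385-388.
- Share of these: 22.5/388 = 5.8% to 67.4/385 = 17.5%.
- NNOLOS quantile (section 5.5): 1.2 × 9.1% = 10.9%, not below 10%, so 10% applies. That is about 1,123 births if the quantile is taken over both arms. Share: 22.5/1,123 = 2.0% to 67.4/1,123 = 6.0%.

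**Why the direction is open**

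Take the crude NMI>=3 odds ratio at 0.023 against 0.036: (0.023/0.977)/(0.036/0.964) = 0.63. Delete stillbirths by replacing each p with (p − r)/(1 − r), where r is the arm's assumed stillbirth rate. Set the control rate at 0.5%, so that the control proportion becomes 0.031/0.995 = 0.0312.

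- Prospective rate 0.5%: 0.018/0.995 = 0.0181, odds ratio 0.57.
- Prospective rate 0.32% (0.5% × 0.023/0.036): 0.0198/0.9968 = 0.0199, odds ratio 0.63.
- Prospective rate 0.2%: 0.021/0.998 = 0.0210, odds ratio 0.67.

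The estimate moves away from the null, stays put, or moves towards it, depending on arm-specific rates that the SAP does not give. This is a crude ratio, not the weighted ordinal model of section 5.5.

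**The case against.** The timing sentence says present, not measured. The named covariate is the maternal disorder, with NOWS as its measure. For the primary list the sentence is therefore imprecise rather than plainly false, and section 5.3 explains that regression gains from adjusting for independent predictors of outcome. That stands. The requirement that covariates be available at the draw governs only the propensity model.

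A reader might infer that the primary model is biased, perhaps in favour of the intervention. The documents do not support this. Deletion needs NOWS coded missing and total missingness below 1%. With 67 stillbirths, 46 missing values from other causes would bring the total to 113, above the limit, and inclusion of NOWS would no longer be guaranteed. The stillbirth rate is assumed, and section 4 does not say whether its 3.6% counts stillbirths. The shares above are illustrations.

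The planned checks help. Section 5.7 compares inclusion and omission of covariates, repeats the primary analysis unadjusted, and repeats it with multiple imputation. These could expose a deletion effect but leave the primary model as it is, and the ITT and completers replications again exclude subjects with missing required variables.

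Coding detail may also sit in a protocol or data dictionary that is not shown. But the SAP itself sets the covariate, the 1% rule and the complete-case rule, and the gap comes from how they combine.

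Two further inferences fail. Gestational diabetes is on the propensity list and is also a descriptive outcome, but the timing sentence already limits the covariate to disease present before the draw. Nor does the SAP show that antenatal substance-use records are held, complete and comparable between arms, so their use cannot be demanded.

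**Conclusion.** The timing text is wrong as written for delivery site, which contradicts both statements in section 5.3. This touches the weighted and matched analyses, not the primary one. For NOWS, the measure is not available at the draw as the propensity model requires, and it cannot be assessed in stillbirths.

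The loss of stillbirths from the primary model is a real interaction of the SAP's own rules, but a conditional one. Under the stated assumptions it would involve about 22-67 births; under the other coding, none. No defect in the primary result is established, and the SAP determines neither the size nor the direction of any bias. Confidence is high for the conflict in wording and lower for its consequence.

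**What to change.** 1. Remove delivery outside ChristianaCare from the propensity model and report it descriptively by arm.
2. Correct the timing sentence: the maternal disorder may predate the draw, but NOWS is ascertained after birth.
3. State that no stillbirth or early death is excluded from the primary or alternative analysis because NOWS could not be assessed, for example through a fixed coding rule.
4. Report the primary model without NOWS alongside, as a named sensitivity analysis. The covariate-omission comparison in section 5.7 already comes close to this.
5. Optionally, use maternal substance use recorded before the draw, but only if it is already held comparably in both arms.

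The cost is SAP wording, one coding rule and one named model run. The downside is that exposure in stillbirths is then set by rule rather than observed, which is a reason to show the model without NOWS beside it.

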The following exploratory endpoints will be evaluated using a time-to-event analysis. The null hypothesis is no difference between historical controls and the prospective arm. The alternative hypothesis is shorter length of stay in the prospective arm as compared to historical controls. Statistical testing for this endpoint will be performed using a Cox proportional hazards regression model with covariates and stratification as specified above for the primary analysis, and with propensity scoring adjustment as specified for the alternative analysis. Length of hospital stay is adjusted to the maximum observed length of stay plus one for all instances of perinatal mortality. Length of NICU stay is adjusted to the maximum observed length of stay plus one for all instances of NICU mortality.

- Reduction in length of NICU hospital stay of all NICU admissions for premature neonates. For clarity, this analysis includes only PTBs with NICU admission. This analysis will be repeated for all premature neonates delivered after spontaneous rupture of membranes or spontaneous onset of labor.
- Reduction in length of NICU hospital stay (including zero-length stays for those not admitted) for all premature neonates from time of birth up to neonatal discharge. For clarity, this analysis includes PTBs independent of NICU admission, with stays for the non-admitted set to zero days. This analysis will be repeated for all premature neonates delivered after spontaneous rupture of membranes or spontaneous onset of labor.

- Reduction in length of neonatal hospital stay for all premature neonates from time of birth up to neonatal discharge. This analysis will be repeated for all premature neonates delivered after spontaneous rupture of membranes or spontaneous onset of labor.

As exploratory analyses, the primary and alternative analyses will be replicated, with the modification that the exploratory analyses will use multiple imputation and will include the candidate variables for which more than 5% of subjects have a missing value.

As exploratory analyses, the primary analysis will be replicated as a “raw” unadjusted analysis, with the modification that no covariates will be included in regressions.

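### Covariates missing in 1–5% of subjects fall between the SAP's inclusion rule and its imputation rule, and the propensity model can lose confounders that nothing restores

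*SAP*

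**What the plan says.** Section 5.3 lists three variables for the primary analysis ("The following variables are candidates for inclusion as covariates in the primary analysis: regression with covariates"): maternal age, parity, and substance use disorder assessed through neonatal opioid withdrawal. A second list gives 15 variables as "candidates for inclusion as covariates in the alternative analysis using inverse probability score weighting" and for propensity matching. Race, BMI, insurance and smoking are on the second list only.

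Four missingness rules then apply:

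- **Inclusion (5.3).** "Inclusion of covariates in the covariate-adjusted primary, alternative and exploratory analyses will depend on the proportion of missing values for the covariate", followed by one criterion: "if fewer than 1% of subjects have a missing value, that variable will be included as a covariate in the analysis".
- **Complete-case cap (5.3).** The primary and alternative analyses use complete cases, "provided that no more than 5% of the total subjects are excluded from the analysis". Beyond that, "candidate variables will be dropped from the analyses in order of the percent missing" until the cap is met. The direction of the order is not stated.
- **Imputed replication (5.7).** The primary and alternative analyses are repeated with multiple imputation, and the repeat "will include the candidate variables for which more than 5% of subjects have a missing value".
- **General statement (5.10).** Where more than one percent of observations are missing, approaches resting on missing at random are used. Mixed-effects models and multiple imputation are named as suitable.

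**The concern.** The thresholds do not meet. Inclusion stops at 1% missing and imputation restores variables only above 5%, so no rule in 5.3 or 5.7 brings in a candidate between the two. Candidates removed by the cap are in the same position: each passed the 1% test, so none exceeds 5%.

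This matters because the comparison is not randomised. Sections 6.1 and 6.2 treat bias as the central analytic problem, and section 5.4 gives the weighted analysis the task of dealing with selection bias. Yet whether a variable enters the propensity model depends on how completely it was recorded, not on whether it confounds. Race, BMI, insurance or smoking could be lost because about 115 records are blank. The adjustment set also stays unknown until missingness is counted, which weakens the prespecification.

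**Working it through.** **Inputs.** Subjects: about 1,453 prospective and 10,000 historical (SAP section 4), total 11,453. Thresholds: 1%, 5% cap and >5%, from 5.3 and 5.7. Candidates: 3 and 15, counted from the lists in 5.3. The SAP states no expected missingness and no number of covariates retained, so there is no figure of its own to reproduce.

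**Width of the gap.** 0.01 × 11,453 ≈ 115 records; 0.05 × 11,453 ≈ 573 records. The percentage is of all subjects, and controls are 10,000/11,453 ≈ 87% of them. A variable complete in the prospective arm but missing in 1.2% of controls (120 records) is missing in 120/11,453 = 1.05% overall, and fails the 1% rule.

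**Primary model.** Three covariates, each under 1% missing, exclude less than 3 × 1% = 3% of subjects. The 5% cap cannot bind.

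**Propensity model.** Let each of the 15 candidates be missing in a share m < 1%. With k variables the excluded share is k·m if different women are affected, 1 − (1 − m)^k if missingness is independent, and m if it overlaps fully. The number kept is the largest k with an excluded share of at most 5%. Dropping the most incomplete variable first is assumed.

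At m = 0.9%, independent: 1 − 0.991^15 = 12.7%, so the cap binds; 1 − 0.991^5 = 4.4% and 1 − 0.991^6 = 5.3%, so five remain.

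| m for every variable | Kept, no overlap | Kept, independent | Kept, full overlap |
|---|---|---|---|
| 0.3% | 15 | 15 | 15 |
| 0.4% | 12 | 12 | 15 |
| 0.5% | 10 | 10 | 15 |
| 0.7% | 7 | 7 | 15 |
| 0.8% | 6 | 6 | 15 |
| 0.9% | 5 | 5 | 15 |

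All 15 remain up to m = 0.05/15 = 0.33% (no overlap) or 1 − 0.95^(1/15) = 0.34% (independent). Only five remain once m exceeds 0.05/6 = 0.83% (no overlap) or 1 − 0.95^(1/6) = 0.85% (independent). If the 15 rates are drawn uniformly from 0 to 1% (an assumption), the median kept is 12, with a 95% range of 9 to 14.

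This is the effect of the cap alone. Candidates at or above 1% would already have been removed, so the 1% rule could take the count below five.

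**Lenient reading.** Suppose under 1% is sufficient but not required. Two candidates each missing in 3%, in different women, exclude 6%. One must go, and at 3% it is below the 5.7 threshold, so imputation does not restore it.

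**Possible bias, with assumed inputs.** A dropped binary confounder with risk ratio 2 and prevalence 10% (prospective) against 15% (controls) gives a spurious ratio of (1 + 0.10)/(1 + 0.15) = 0.957. The planned ratio for a neonatal index of 3 or more (section 4) is 0.020/0.036 = 0.56 to 0.023/0.036 = 0.64.

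**The case against.** The strongest reply is that 5.3 states a sufficient condition and never says that only such variables enter. On that reading a variable missing in 1–5% may enter subject to the cap, and one above 5% must break the cap by itself, which would explain why 5.7 restores exactly that group. The cap is also applied to the primary analysis, where it would be idle under the strict reading. This is a fair argument. But the 1% threshold would then do no work, the lead-in to the rule presents it as the inclusion criterion, and variables removed by the cap would still not return.

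A reader might infer that a variable with 1–5% missing disappears from every analysis. The documents do not support that:

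- 5.10 points to missing-at-random methods above 1%, and 5.3 promises missing-data sensitivity work. Neither names a model or a variable, so they conflict with the gap and do not close it.
- Some treatment, compliance and bootstrap repeats in 5.7 re-admit listed variables with no missingness threshold. They do so only if an association is found, only in exploratory or sensitivity work, and still exclude subjects with missing values.
- Baseline imbalance in a dropped variable would still be reported in the descriptive comparison under 5.3.

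It also stands that covariates are not the only safeguard. Section 5.7 plans analyses within the prospective arm, including one at the risk-score threshold, that do not use historical controls. Section 5.10 expects few missing values. A complete-case analysis with a small, capped loss is in itself a defensible choice for the primary test.

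**Conclusion.** The point holds as a gap between rules. On the natural reading of 5.3 and 5.7, candidates missing in 1–5% of subjects enter neither the primary, weighted and matched analyses nor the imputed replication, and 5.10 says something different. On either reading, candidates missing in 5% or fewer that the cap drops are not restored.

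The consequence lies mainly in the propensity analyses. A reader might infer that the primary analysis loses BMI, smoking, insurance or race. It does not, because they are not candidates there. A reader might also take five of 15 as the expected outcome. It is the worst case of the cap, needing every variable just under 1% missing with little overlap. Overlap is plausible, since the two BMI variables share a source and several others are obstetric-history counts. The range is 5 to 15, and the actual loss cannot be determined from the SAP.

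The bias from one lost confounder under the assumed inputs is small (0.96). Three would give 0.957³ ≈ 0.88, but that needs three independent confounders of that strength, all imbalanced in the same direction and all dropped. Nothing in the SAP establishes this.

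**What to change.** In the alternative (weighted) and matched analyses, stop selecting prespecified confounders by completeness. Keep all 15 listed candidates, multiply impute missing baseline values, and report the complete-case version as the sensitivity analysis.

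At a minimum:

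1. Change 5.7 so that the imputed replication of the primary and alternative analyses includes every prespecified candidate not already in the model, whatever its missingness.
2. Reconcile 5.3 with 5.10, so that one rule governs covariates above 1% missing.
3. If the cap is kept anywhere, state the direction in which variables are dropped.

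Moving imputation into the primary test is not needed. It is more debatable, and the cap is already idle there under the 1% rule.

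The cost is SAP wording and some additional imputation work, with reliance on missing at random, which 5.10 already assumes.
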